7.2.4. Day x (Day of pneumonia)

The day when a diagnosis of established pneumonia or possible pneumonia is made, will be called Day x. Treatment against *P. aeruginosa* pneumonia will be initiated as soon as the diagnosis is confirmed or if this pathogen is considered as a highly likely cause of pneumonia. The Day x procedures will be implemented as completely as possible on that day (similar to Day n-1) and the remaining items will be performed the next day (Day n). The patient will not receive the test drug on the following morning and the patient will be discharged from the study on Day n with safety and physical examination.

In case of suspicion of pneumonia the necessary explorations will be performed in order to lead to a confirmed diagnosis based on the criteria for *P.aeruginosa* summarized in the table presented below:

Investigation	Documented Pneumonia Day x
BAL	$\geq 10^4$ CFU/mL
Or tracheobronchial aspirate	$\geq 10^5$ CFU/mL
Or protected brush specimen (PBS)	$\geq 10^3$ CFU/mL
CPIS* (see detailed score in App. I)	≥ 6

The diagnosis of pneumonia will be confirmed at later stage under double blind conditions by a panel of independent clinical experts prior to stopping the study to ensure that 10 documented cases of *P. aeruginosa* pneumonia have been included in the study for assessment. The data provided will be patient characteristics, symptoms, all CPIS parameters generated, CPIS overall scores, all X-rays collected and results of BAL (or tracheobronchial aspirate or protected brush). Efforts will be made to achieve a total of 10 pneumonia cases in patients who do not receive concomitant therapy with an antibiotic with activity against the isolated *P. aeruginosa* strain, providing however the overall constraint for a maximum of 240 patients entered will not be trespassed.

Post treatment activities will include:

- Tracheal aspirate 2 (for freezing and transfer to Geneva laboratory for investigation), collected early afternoon (usually 6 hours [if Day x] or 30 hours [if Day n and if applicable] after last test drug administration) if patient still intubated and even if antipseudomonal antibiotherapy has been meanwhile initiated
- ECG, 1 to 4 hours late morning Day x
- Blood pressure, heart rate, respiration rate (early afternoon Day x or Day n)
- Lung X-ray whenever possible that day

- Body temperature (tympanic or rectal) ~17:00
- Local tolerance (up to 24 hours)
- Systemic tolerance (up to 24 hours)

Physical examination and laboratory safety parameters (blood and urine) will be collected on Day n.

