1. INTRODUCTION AND RATIONALE FOR STUDY DESIGN

1.1 Introduction

Patients who are referred to the intensive care unit (ICU) for mechanical ventilation have serious conditions, e.g. surgical complications after visceral, cardiovascular or pulmonary interventions, transplantation, multiple or thoracic trauma, acute respiratory distress syndrome (ARDS) elicited by aspiration, inhalation of chemicals, overdose of narcotics or sepsis, or deterioration of underlying disease such as congestive heart failure (CHF) or pulmonary insufficiency. These patients are very fragile and frequently develop ventilator associated pneumonia (VAP), a complication responsible for a high mortality (~40%) and for high costs due to further prolongation of their intubation period.

Pseudomonas aeruginosa is one of the three major Gram-negative pathogens associated with VAP and is especially feared. The virulence of this pathogen has been suggested to be, at least partially, due to quorum sensing, a system based on the production of diffusible autoinducer molecules which synchronize the production of virulence factors once a high cell density is achieved. This complex mechanism of virulence explained in detail below in Section 1.2 leaves very limited time to the host for mobilizing his immune system against this orchestrated attack. Quorum sensing is also responsible for the development of bacterial biofilms and for colonization of inert surfaces, a prerequisite to pneumonia. The colonization of the intubation device is believed to precede colonization of the respiratory tract, and to lead in a subset of patients to a *P. aeruginosa* VAP. Since colonization almost always precedes pneumonia, the presence of *P. aeruginosa* in lung secretions is not considered as diagnostic for VAP. In the case of clinical suspicion of VAP, state-of-the-art care requires to quantify *P. aeruginosa* on samples collected by bronchial alveolar lavage (BAL), by protected brush specimen (PBS) or by bronchotracheal aspirate, thus delaying the confirmation of the diagnosis.

Intrinsic resistance of *P. aeruginosa* to many antibiotics is well documented and the antibiotics with antipseudomonal activity cannot be used prophylactically due to the high risk of resistance emerging during treatment. Moreover no treatment can eradicate the pathogen from the intubation device as long as it is remaining in place.

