* Except if isolated *P. aeruginosa* strain resistant or if medically indicated

Patients on antibiotherapy with activity against pseudomonas prior to study entry will be maintained in the screening phase for 48 hrs, pending results of the antibiogram on the colonized strain. If found to be susceptible to the antibiotic used, the patient will be excluded from the study; if resistant, the patient will be included in the study. Patients already included in the study but requiring an antibiotic with activity against the colonizing *P.aeruginosa* strain will be maintained in the study. Statistical analysis will be performed in these patients as a subgroup and combined with remaining patients only if the pattern of response between treatments is found to be similar to patients treated with no antibiotics or with antibiotics deprived of antipseudomonal activity.

When suspicion of *P.aeruginosa* pneumonia is raised by the clinical situation, a diagnostic procedure must be performed (BAL, PBS) before an antibiotic with antipseudomonal activity can be given empirically. In the case *P.aeruginosa* pneumonia has been diagnosed (Day x) by quantitative culture, dedicated antibiotherapy to treat *P.aeruginosa* infection is recommended and the patient should be taken out of the study at that stage.

Except for other macrolides no treatment is forbidden during the study as reflected in the inclusion/exclusion criteria. Few clinically significant drug interactions are expected to impact on azithromycin clearance, metabolism or distribution and thus concomitant therapy should not influence the clinical outcome of this study. However it is prudent to monitor plasma concentration of concomitant drug which could be increase, thus leading to toxicity, when administering:

- Drugs such as theophyllin, digoxin, ergotamine, dihydroergotamine, or triazolam
- Compounds metabolized by cytochrome P450 system such as carbamazepine, cyclosporine, hexobarbital or phenytoine
- Drugs known to increase QTc wave such as selected H1-antihistaminics
- During therapy with anticoagulants such as warfarin should be monitored regularly by prothrombin time as performed in this study

Dosages of concomitant drugs should be adapted for the best interest of the patient if required for efficacy and/or safety reasons.

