7.1.2. Pharmacodynamic data performed in local laboratory

A. Tracheal aspirates (on Aspirate 1)

- Collection daily
- Quantitative culture for *P. aeruginosa* (CFU/mL) on Day -1, 1, 3, 6, 9, 12, 15, 18 and last day (Day x, or Day n-1, or Day 20)
- Isolate *P. aeruginosa* strain daily and store at -70°C on skim milk and glycerol
- Emergence of resistance (MIC to *P. aeruginosa* in tracheal aspirate for 11 standard antipseudomonal antibiotics on Day -1 and on last day (Day x, or Day n-1, or Day 20) see list under Section 6.2)
- CFU for other strains from tracheal aspirates if indicated

B. BAL on Day x (or protected brush specimen (PBS) or bronchotracheal aspirate)

- Only for patients with suspected pneumonia for diagnosis
- CFU/mL
- Cellularity

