7.3. Methods of evaluation

Clinical efficacy (clinical site)

All clinical variables will be collected at the clinical site, within the ICU, by a designated subinvestigator and ICU nurse, whenever possible by the same individuals for a given patient, barring emergencies.

Pharmacodynamic data (local laboratory)

Selected pharmacodynamic data (tracheal aspirate 1: quantitative count for *Pseudomonas aeruginosa* on Day -1, 1, 3, 6, 9, 12, 15, 18 and last day (Day x, or Day n-1, or Day 20), MIC to *P.aeruginosa* for 11 standard antipseudomonal antibiotics on Day -1 and on last day (Day x, or Day n-1, or Day 20) (see list in Section 6.2), CFU for other strains if indicated; BAL: CFU/mL, cellularity) will be performed in local bacteriology laboratory on a daily basis. MIC will be performed by one standard assay (disk diffusion assays as defined by the NCLS (National Committee for Laboratory Standards, or E-test, or dilution). All parameters will be assessed under double blind conditions for treatment.

Pharmacodynamic data (Geneva laboratory)

Extensive pharmacodynamic data both *in vivo* (tracheal aspirates 2: content for autoinducers,; mRNA for lasB elastase (lasI, rhlI); BAL: CFU/mL, autoinducer content; Respiration device: CFU/cm², autoinducer content) and *in vitro* (isolated strains from tracheal aspirates prepared by local laboratory, BAL and respiration device: virulence factor production, autoinducer production, azithromycin gradient plates for detection of rhamnolipid production) will be performed in the laboratory of [name] [name], Department of Genetics and Microbiology, Medical School, University of Geneva, Switzerland).

This list is provided as an example only and final parameters finally agreed upon may differ and will be described in a separate document which will be produced before unblinding the study and will be attached to the final Clinical Study Report. Details on samples to be analyzed are provided in Section 7.2.3. The control patients will be selected by an independent physician who will be given access to the allocation code, pairing 2 control patients by site (1 treated with azithromycin, 1 treated with placebo) with a pneumonia patient, but not by sex or age if not achievable. All parameters will be assessed under double blind conditions for treatment allocation, but not for study day.

Laboratory safety

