APPENDIX E

Collection and Assessment of Bronchial Alveolar Lavage (BAL),

Bronchotracheal Aspirate or Protected Brush Specimen (PBS) on Day x

Material

- Sterile fibroscope tip or sterile protected specimen brush
- Sterile catheter
- Sterile saline (0.9 % sodium chloride)
- Special double walled tubes for microbiology 200 mL of adequate size, with screw caps for storage and transport of infectious specimens
- Labels to be printed by Quintiles

Collection of BAL (or bronchotracheal aspirate or PBS)

1. Depending on clinic setup, ICU routine, and patient condition, 3 different techniques may be used on the presumed Day x for confirming diagnosis of pneumonia:
 - Bronchoalveolar lavage (BAL)
 - Bronchotracheal aspirate
 - Protected brush specimen (PBS)
2. A BAL specimen will be taken only if there is strong suspicion of pneumonia to confirm diagnosis (Day x). This procedure should be performed by a trained intense care physician, only if medically not contraindicated, under aseptic conditions and operating as fast as possible to minimize the period when the patient is weaned off from mechanical ventilation. The procedure must be completed fast, using the routine, standardized procedure of the ICU and maintaining as aseptic conditions as possible during aspiration, collection and transfer of BAL specimens to the labeled storage tubes
3. Apply 100% O₂ bagging technique just before shifting the fibroscope or the brush through the tracheal tube
4. The fibroscope tip or brush will be positioned in a segmental ostium (lingual or right middle lobe), the selected side depending on the opacities seen on the lung radiography
5. In case of BAL, 2 aliquots of 50 mL of tepid saline will be infused through the aspiration port and collected via the same port by suction to collect the BAL fluid in 2 sterile tubes:
 - 1 tube will be sent to local laboratory for CFU analysis for diagnostic purposes, centrifugation, and differential cytology
 - 1 tube will be stored at -70 °C pending shipment to Geneva for special analysis (see Section 7.2.3)
6. If the protected brush technique is used, the brush will be disengaged from its sheath when *in situ*, gently sweeping the bronchial wall upon withdrawing. This specimen will be kept for local laboratory assessment. No specimen for the Geneva laboratory will be available using this technique
7. The patient will be put immediately back onto the mechanical ventilation as soon as the procedure is completed

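### Day x is the specimen day in some sections and the diagnosis day in others, so time to pneumonia is dated inconsistently and the cases' last-day count and MIC may be taken under antipseudomonal therapy

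*Protocol*

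**What the plan says.** The Protocol uses Day x in two ways.

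- **Specimen day.** Section 7.1.2 lists "BAL on Day x (or protected brush specimen (PBS) or bronchotracheal aspirate" among the local laboratory data. Appendix E says that "3 different techniques may be used on the presumed Day x for confirming diagnosis of pneumonia", and its label specification puts Day x on the specimen tube together with the sampling time and date.
- **Diagnosis day.** Section 7.2.4 states "The day when a diagnosis of established pneumonia or possible pneumonia is made, will be called Day x". Section 6.2 refers to the case where *P. aeruginosa* "pneumonia has been diagnosed (Day x) by quantitative culture".

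The Introduction (1.1) says that quantifying the organism is required on suspicion, "thus delaying the confirmation of the diagnosis".

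Section 6.2 permits empirical antipseudomonal treatment once the diagnostic procedure has been done. Section 7.2.4 permits treatment when the pathogen is thought highly likely. Section 7.2.4 also has aspirate 2 collected "even if antipseudomonal antibiotherapy has been meanwhile initiated".

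For a pneumonia case, Day x is the last day. Section 7.3 schedules the MIC "for 11 standard antipseudomonal antibiotics on Day -1 and on last day". Section 7.1.2 schedules the aspirate 1 count on Days -1, 1, 3 and every third day to 18, and on the last day. The synopsis lists time to pneumonia with Day x as its date.

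**The concern.** If specimen day and diagnosis day differ, two sites with identical patients record different dates for the same pneumonia. The primary objective covers delaying pneumonia as well as preventing it, and time to pneumonia is the variable that measures delay.

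The same ambiguity decides when the Day x sample set is taken. A site that treats the specimen day as Day x takes aspirate 1 around the time of the diagnostic procedure. A site that waits for the culture takes it a day or more later, possibly after an active antibiotic has begun. The count and the MIC pattern could then reflect that antibiotic rather than the state at pneumonia. The MIC change from Day -1 to the last day is the protocol's measure of emerging resistance, and only about 10 cases are planned.

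**Working it through.** **1. Can the two usages be the same day?** The middle ground would be to read the possible pneumonia of Section 7.2.4 as a bedside suspicion made on the specimen day. Appendix I does not support this: it defines possible pneumonia as a CPIS of 6 or more with a count below the threshold, so that category also needs the culture result. Section 1.1 says that this result comes with delay. Specimen day and diagnosis day are therefore different days.

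**2. The protocol's own timing figure.** Section 7.2.4 puts aspirate 2 at 6 h after the last dose if taken on Day x and 30 h if on Day n. With Day n = Day x + 1, 6 + 24 = 30 h, which reproduces the figure. It fits only if Day n follows Day x. Section 7.2.3, however, lists Day x among the days that Day n may correspond to.

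**3. Size of the dating difference.** No lag is given, so L = 1, 2 or 3 days is an assumption. Shift as a share of the 20-day maximum = L/20. For antibiotic exposure, also assume a specimen at 14:00, treatment starting at once, and on the result day aspirate 1 at 08:00 and aspirate 2 at 14:00. Hours on antibiotic are then 24L − 6 before aspirate 1 and 24L before aspirate 2.

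| L (days) | Shift in time to pneumonia | Before aspirate 1 | Before aspirate 2 |
|---|---|---|---|
| 1 | 1 day (5%) | 18 h | 24 h |
| 2 | 2 days (10%) | 42 h | 48 h |
| 3 | 3 days (15%) | 66 h | 72 h |

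**4. What can be recovered afterwards?** Section 7.1.2 has strains isolated and stored daily, so an MIC can still be run on an earlier strain. A count cannot be obtained from a stored strain. Within Days 1 to 20, counts are scheduled on Days 1, 3, 6, 9, 12, 15, 18 and 20, which is 8 days. The other 20 − 8 = 12 days follow the Day 2 pattern in Section 7.2.3, with neither a count nor a CPIS. If the specimen falls on one of those 12 days and the site treats the result day as Day x, no aspirate 1 count or CPIS is scheduled for the specimen day.

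**5. Which data are already protected?** Section 7.1.3 schedules the Geneva assays daily for pneumonia patients and for patients on antibiotics. Pre-antibiotic autoinducer and virulence values should therefore exist for the cases.

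**The case against.** The strongest reply is that little of consequence depends on the date. The primary variable is occurrence, yes or no, compared by Fisher's exact test (11.3), and a blinded panel confirms each case from the CPIS, X-ray and culture data (7.2.4). A reader might infer that the primary count changes with the reading of Day x. The documents do not support that in general. Results arriving after Day n are also not lost, because Sections 7.2.6 and 8.2 collect clinical outcome to Day n+7. What stands is narrower: nothing says whether a specimen taken near Day 20 or extubation, with a later result, is an on-study event.

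A reader might also infer that the quorum-sensing objective is compromised. The daily Geneva assays largely answer this. Collecting aspirate 2 after antibiotics have started is an open choice in Section 7.2.4, not an oversight.

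Nor is bias between arms shown. Allocation is double-blind and balanced within site in blocks of 4 (5.3), so a site's reading of Day x applies to both arms. The expected effect on time to pneumonia is added noise.

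Finally, the 48 hours in Section 4.3 is the wait for an antibiogram on the colonizing strain at screening, and is no estimate of the delay for a diagnostic count.

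The textual conflict survives all of this, as do the exposed last-day count and MIC.

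**Conclusion.** The inconsistency is real and worth correcting, but its reach is limited to secondary data. Time to pneumonia is dated differently according to the section a site follows, by the length of the culture lag: 1 to 3 days, or 5% to 15% of the 20-day window, if that lag is assumed. The cases' last-day aspirate 1 count and MIC may be taken after antipseudomonal treatment has begun; the 18 to 66 h before aspirate 1 is illustrative and rests on the assumed lag and clock times.

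It is tempting to go further and say that all 10 cases would have treated last-day samples, or that about one in ten would be sampled before Day 20 and confirmed after it. The first is only a ceiling. The second needs a 2-day lag and evenly spread onset, which the protocol does not give and which departures through extubation and death make doubtful. Neither should be used.

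**What to change.** - **One analysis date.** For analysis, date pneumonia by the calendar day on which the diagnostic specimen that met the criteria was collected. State this in 7.2.4 and align 6.2, 7.1.2 and Appendix E.
- **Last-day MIC and CFU in cases.** Use the last aspirate 1 collected before the first antipseudomonal dose: the stored strain for MIC, and the count where available. Flag later samples as post-antibiotic.
- **Close the gap in counts.** Request the aspirate 1 count and a CPIS on any day a diagnostic specimen is taken.
- **Event window.** State that a qualifying specimen collected up to Day n is an on-study event, whatever day the result arrives.
- **Reconcile separately.** Section 7.2.3 ends study drug when the diagnosis is confirmed; 7.2.4 withholds it from the morning after Day x. Section 7.2.3 lets Day n coincide with Day x; 7.2.4 puts it afterwards. The sponsor must reconcile these. No clinical rule is proposed, and the analysis date should not be made the trigger for them, because it is known only once the culture is read.

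The cost is protocol and CRF wording, plus a few extra counts and CPIS scores for suspicions that prove negative. Aspirate 1 and strain storage are already daily. The small downside is that the analysis date is assigned retrospectively.

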- Body temperature (tympanic or rectal) ~17:00
- Local tolerance (24 hours)
- Systemic tolerance (24 hours)

Day 3

On the morning of Day 3, prior to infusion of test drug, the following procedures will be performed:

- Adverse events from previous night
- Local tolerance
- Body temperature (tympanic or rectal) ~7:00
- Blood pressure, heart rate, respiration rate (~8:00)

- Blood (see Appendix B)
 - Hematological profile
 - Blood chemistry
 - WBC, CRP
- Specimen for blood culture (only if clinically indicated)
- Blood gases
- Oxygenation: PaO₂/ FI_{O2}
- CPIS (use results of lung X-ray of same day whenever possible)
- Clinical endpoints
- Tracheal aspirate 1 (transfer to local laboratory, for parameters see Section 7.1.2 above)
 - Quantification of *P. aeruginosa* (CFU/mL)
 - Isolation of *P. aeruginosa* strain (storage -70°C)

After these activities, the test drug will be infused over 1 hour, usually from 8 to 9 o'clock.

Post treatment activities will include:

- ECG, 1 to 4 hours post infusion start
- Tracheal aspirate 2 (for freezing and transfer to Geneva laboratory for investigation), collected ~6 hours post infusion start
- Blood pressure, heart rate, respiration rate (~6 hours post infusion start)
- BAL if required medically
- Lung X-ray whenever possible during the day
- Body temperature (tympanic or rectal) ~17:00
- Local tolerance (24 hours)
- Systemic tolerance (24 hours)

Subsequent study days in 3 day cycles (Day 4, 5 & 6; Day 7, 8 & 9; Day 10, 11 & 12; etc.)

This same treatment and sampling policy, using a 3-day cycle will be used until Day n which may correspond to Day 21 (24 hours after last treatment day i.e. after 20 days of treatment), or to extubation day because mechanical ventilation is medically not required any longer, or to exitus day (due to underlying disease complication, infection due to any strain type and site with or without sepsis, *P. aeruginosa* infections of non pulmonary location) and finally to Day x when *P. aeruginosa* pneumonia diagnosed.

The procedures to be performed daily or every third day are summarized in the Study Schedule (page 10) and as briefly reviewed below:

Day 4, 5, 7, 8, 10, 11, 13, 14, 16, 17, 19	Correspond to Day 2
Day 6, 9, 12, 15, 18	Correspond to Day 3
Day x (pneumonia, see below)	Corresponds to Day 3 with some additional parameters and study drug is terminated once diagnosis confirmed
Day n-1 or Day 20	Corresponds to Day 3, and is last day of test drug (with some additional parameters)

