APPENDIX I

Clinical Pulmonary Infection Score (CPIS)

This Clinical Pulmonary Infection Score (CPIS) has been originally developed by Pugin et al (1991), and later adapted by Singh et al (2000) to diagnose pneumonia on the basis of 7 parameters listed in the table below with the appropriate scoring system (for details on measurements, see Study Schedule on page 10 and Section 7.1.2):

Item	Units	Score 0	Score 1	Score 2
Body temperature	°C	≥36.5 and ≤38.4	≥38.5 and ≤38.9	≥39.0 or ≤36.0
Blood leukocytes	mm ³	≥4'000 and ≤11'000	<4'000 and >11'000	<4'000 and >11'000 and band forms ≥ 50%
Tracheal secretions		Absent	Present Non purulent	Present Purulent
Oxygenation Pa _{o2} /Fi _{o2}	mm Hg	>240 or ARDS*	--	≤240 and no ARDS*
Lung X-ray infiltrate		Absent	Diffuse or patchy	Localized
Progression of lung infiltrate		No progression	--	Progression (after CHF and ARDS excluded)
Tracheal aspirate culture (predominant pathogen)		None or rare or +	Moderate or heavy in culture	Same organism on Gram stain

ARDS = Acute respiratory distress syndrome

Defined as Pa_{o2}/Fi_{o2} ≤200, pulmonary wedge pressure ≤18, and acute pulmonary infiltrates

CHF = Congestive heart failure

Patients with a total CPIS for *Pseudomonas aeruginosa* of:

- <6 are unlikely to have pneumonia
- ≥6 have pneumonia
 - IF BAL ≥10⁴ CFU/mL and possible pneumonia if lower
 - OR if bronchotracheal lavage ≥10⁵ CFU/mL and possible pneumonia if lower
 - OR if protected specimen brush ≥10³ CFU/mL and possible pneumonia if lower

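### The CPIS table that gates the primary event cannot be scored as printed, and the protocol disagrees with itself on whether possible pneumonia ends study drug

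*Protocol*

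**What the plan says.** The primary variable is the occurrence of *P. aeruginosa* pneumonia (Section 7.1.1), compared by Fisher's exact test at two-sided 0.10 (Section 11.3). Recruitment stops at ten cases confirmed by a blinded panel (Section 4.1), within a ceiling of 240 patients (Section 7.2.4).

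**Case definition.** The table in Section 7.2.4 lists, for documented pneumonia, a culture threshold (BAL 10⁴, tracheobronchial aspirate 10⁵ or protected brush 10³ CFU/mL) and CPIS of 6 or more. Appendix I sorts patients into three classes. Below 6, pneumonia is unlikely. At 6 or more with a culture at threshold, the patient has pneumonia. At 6 or more with a lower count, pneumonia is possible.

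**Score table (Appendix I).** Leukocyte score 0 covers 4,000 to 11,000 per mm³. The cell for score 2 reads "<4'000 and >11'000 and band forms ≥ 50" per cent, and score 1 has the same count condition without the band forms. Temperature scores 0 for "≥36.5 and ≤38.4" °C, 1 for 38.5 to 38.9, and 2 for 39.0 and above or 36.0 and below.

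**Day x.** Section 7.2.4 says "The day when a diagnosis of established pneumonia or possible pneumonia is made, will be called Day x", and then "The patient will not receive the test drug on the following morning and the patient will be discharged from the study on Day n". For Day x, the summary of procedures in Section 7.2.3 says "study drug is terminated once diagnosis confirmed". Section 6.2 speaks of the case where "pneumonia has been diagnosed (Day x) by quantitative culture". The panel's confirmation takes place "prior to stopping the study to ensure that 10 documented cases of" *P. aeruginosa* pneumonia exist.

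**The concern.** A trial that ends on ten events depends on every site applying the event rule in the same way. Here 20 sites are targeted and up to 25 provided for (Section 5.3), and all of them score from one table. Where that table gives no valid score, each site must improvise. Two sites can then place the same patient on opposite sides of the cut-off of 6.

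The second problem concerns patients who reach 6 but whose culture is below threshold. Under one section they come off drug and leave the study. Under another they stay on drug until the diagnosis is confirmed. If they leave, scheduled surveillance ends because the endpoint itself is suspected, so the loss of observation is related to the outcome being measured. The protocol does not say what status such a patient has in the primary comparison.

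**Working it through.** **1. The plan's own figure.** Section 11.5 derives 100 to 200 assessable patients from ten cases and a 10% placebo rate. With equal arms, N = 2 × (placebo cases ÷ 0.10). A 5:5 split gives 2 × 50 = 100, and a 10:0 split gives 2 × 100 = 200. Both are reproduced. The result will rest on about ten classified events.

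**2. Leukocyte row, read literally.** No number is both below 4,000 and above 11,000, so no count meets score 1 or score 2. A count of 4,000 to 11,000 scores 0. Any count outside that range meets none of the three cells and has no score.

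**3. Effect on the cut-off if sites give such counts no points.** Inputs are the seven items of Appendix I. Five can score 0, 1 or 2 (temperature, leukocytes, secretions, infiltrate, culture). Two can score only 0 or 2 (oxygenation, progression).

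- Profiles: 3⁵ × 2² = 972. Maximum: 7 × 2 = 14, or 12 without leukocyte points.
- The six items other than leukocytes give 3⁴ × 2² = 324 combinations. Of these, 191 total 6 or more, 52 total 5 and 40 total 4.
- With leukocyte points never given, profiles reaching 6: 3 × 191 = 573.
- With the row read as below 4,000 *or* above 11,000, a subtotal of 5 also reaches 6 with 1 or 2 leukocyte points (2 × 52 = 104), and a subtotal of 4 reaches 6 with 2 points (40). Total: 573 + 104 + 40 = 717.
- Difference: 717 − 573 = 144 of 972 profiles.

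These are unweighted counts of possible score combinations. They are not frequencies of patients.

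**4. Temperature row.** Recorded to one decimal, 36.1, 36.2, 36.3 and 36.4 °C match no band. The neighbouring bands score 0 and 2. Whether such a patient reaches 6 depends on that choice when the other six items total 4 or 5, which is 40 + 52 = 92 of 324 combinations (again unweighted, with the leukocyte row read as *or*).

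**5. The Day x passages side by side.**

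| Section | What makes Day x or ends drug |
|---|---|
| 7.2.4 | established or possible pneumonia; no drug next morning; discharge on Day n |
| 7.2.3 | drug ends on confirmation of the diagnosis |
| 6.2 | Day x attached to diagnosis by quantitative culture; patient then taken out |

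The direct conflict is between 7.2.3 and 7.2.4. Section 6.2 uses Day x in the narrower sense but does not say that nothing else can end participation.

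**6. Following one possible case.** Suppose CPIS is 6 or more and the culture is below threshold. Appendix I calls this possible pneumonia, and Section 7.2.4 makes it a Day x. Drug stops, and the patient is discharged from the study on Day n. The scheduled aspirates, cultures and CPIS, which could have run to Day 20, end there. Afterwards only the Day n+7 information of Section 7.2.6 is collected, by visit or report. The panel and the stopping rule count documented cases. Sections 11.2 and 11.3 do not mention possible cases.

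**The case against.** Several points on the other side are sound.

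- **The leukocyte condition is a visible slip.** Score 0 covers exactly the middle range, so most readers will supply *or*. That is likely, but it does not help with the temperature gap, which the table itself cannot resolve. A reader might also infer that an abnormal count always scores 0 as printed. It does not: score 0 is reserved for normal counts. The loss of points in step 3 is a consequence only if sites award none.
- **A blinded panel confirms the cases.** Section 7.2.4 gives it the individual CPIS parameters, overall scores, X-rays and culture results. This is a real safeguard and may limit the scoring fault. But the panel is given no rule for rescoring and none for possible cases.
- **Possible cases are not lost.** Day n+7 outcome, including pneumonia, is collected even for patients on antipseudomonal treatment. Follow-up is shortened and less structured, but it is not absent.
- **Their analysis can be settled later.** Section 11.3 promises a detailed statistical plan before decoding. That plan is not at hand, so its content is no criticism. A reader might infer that possible cases are analysed as pneumonia-free; the protocol does not say so.
- **The missing connector in the Section 7.2.4 table is not a contradiction.** The CPIS row cites Appendix I, which requires both conditions.

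**Conclusion.** The concern holds in two limited parts.

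First, the score table behind the primary event is wrong as written in two of its seven items. The size is conditional: if the leukocyte row earns no points, 144 of 972 unweighted profiles fall below the cut-off. How many patients that means cannot be derived from the protocol. This assumes the printed table reads as in the text at hand; the same conjunction stands in both leukocyte cells.

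Second, Sections 7.2.3 and 7.2.4 conflict on what ends study drug, Section 6.2 uses Day x more narrowly, and the place of possible cases in the primary comparison is not stated in the protocol.

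Two stronger conclusions are tempting. One is that the scoring faults move patients between documented and possible pneumonia. They do not: both classes need CPIS of at least 6, and the culture threshold separates them. The faults move patients between unlikely pneumonia and those two classes. The other is that dropping a single case from ten would decide the test. The documents do not support that as a general statement, because recruitment continues until ten cases are confirmed or the 240 ceiling is reached, and no number of possible cases is given.

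The correction is worth making because the rule decides the primary variable and costs almost nothing to repair.

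**What to change.** 1. In Appendix I and the CRF score sheet, change the leukocyte condition to below 4,000 *or* above 11,000 for scores 1 and 2, with score 2 adding the band-form condition. Assign temperatures between 36.0 and 36.5 °C to one band. Do both before unblinding.
2. Have the blinded panel rescore CPIS from the raw values with the corrected table.
3. For clarity, repeat in Section 7.2.4 that a documented case needs a culture threshold and CPIS of at least 6.
4. Reconcile Sections 6.2, 7.2.3 and 7.2.4 on what constitutes Day x and what ends study drug. Which rule to adopt is a clinical decision and is not proposed here.
5. State that possible cases go to the blinded panel, using the Day n+7 outcome and any culture and X-ray results from routine care. Add a supportive Fisher analysis counting documented or possible pneumonia as events, in the protocol or in the promised statistical plan.

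The cost is text and CRF edits, some panel time for rescoring and for possible cases, and one supportive analysis. No additional X-rays or aspirates after discharge are asked for.
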